7.3.12.2. Female Participant Reproductive Inclusion Criteria

A female subject is eligible to participate if she is not pregnant or breastfeeding, and at least1 of the following conditions applies:

• Is not a woman of childbearing potential (WOCBP) (see definitions below in Section 7.3.12.3).

OR

• Is a WOCBP and using an acceptable contraceptive method as described below during the intervention period (for a minimum of 90 days after the last dose of study intervention). The investigator should evaluate the effectiveness of the contraceptive method in relationship to the first dose of study intervention. The investigator is responsible for review of medical history, menstrual history, and recent sexual activity to decrease the risk for inclusion of a woman with an early undetected pregnancy.

7.3.12.3. Women of Childbearing Potential

Women of childbearing potential includes any female who is fertile, following menarche and until becoming postmenopausal unless permanently sterile. Permanent sterilization methods include hysterectomy, bilateral salpingectomy, and bilateral oophorectomy.

Postmenopausal is defined as no menses ≥ 12 months with or without an alternative medical cause. In addition, a high follicle-stimulating hormone level in the postmenopausal range must be used to confirm a postmenopausal state in women not using hormonal contraception or hormonal replacement therapy.

7.3.12.4. Contraception Methods

Below are the general contraceptive methods (which are both highly and non-highly effective) use by men or women should be consistent with local availability/regulations regarding the use of contraceptive methods for those participating in clinical trials.

- 1. Intrauterine device.
- 2. Intrauterine hormone-releasing system.

- 3. Bilateral tubal occlusion.
- 4. Vasectomized partner:
 - Vasectomized partner is a highly effective contraceptive method provided that the partner is the sole sexual partner of the woman of childbearing potential and the absence of sperm has been confirmed. If not, an additional highly effective method of contraception should be used. The spermatogenesis cycle is approximately 90 days.
- 5. Combined (estrogen- and progestogen-containing) hormonal contraception associated with inhibition of ovulation:
 - Oral
 - Intravaginal
 - Transdermal
- 6. Progestogen-only hormone contraception associated with inhibition of ovulation:
 - Oral
 - Injectable
 - Implantable
- 7. Sexual abstinence:
 - Sexual abstinence is considered a highly effective method only if defined as refraining from heterosexual intercourse during the entire period of risk associated with the study intervention. The reliability of sexual abstinence needs to be evaluated in relation to the duration of the study and the preferred and usual lifestyle of the subject

7.3.13. Adverse Events of Special Interest

There are currently no identified AESI for PTC857.

7.3.14. Medication Errors

Medication errors may result from the administration or consumption of the study intervention by the wrong subject, or at the wrong time, or at the wrong dosage strength.

Table 9: Investigator Site Requirements for Recording/Reporting Medication Errors

| Event | Recorded on the eCRF | Reported to the PTC Pharmacovigilance Department Within 24 Hours of Awareness |
|-------------------|---|---|
| Medication errors | All (regardless of whether associated with an AE) | Only if associated with an SAE |

Abbreviations: AE, adverse event; eCRF, electronic case report form; SAE, serious adverse event

Medication errors include the following:

• Medication errors involving subject exposure to the study intervention

- Potential medication errors or uses outside of what is foreseen in the protocol that do or do not involve the study subject
- The administration of expired study intervention
- The administration of an incorrect study intervention
- The administration of an incorrect dosage
- The administration of study intervention that has undergone temperature excursion from the specified storage range, unless it is determined by PTC that the study intervention under question is acceptable for use.

Such medication errors occurring to a study subject are to be captured in source and eCRF as applicable.

Whether or not the medication error is accompanied by an AE, as determined by the investigator, the medication error is recorded on source and, if applicable, any associated AE(s), serious and nonserious, are recorded on the AE page of the eCRF. Medication errors should be reported to the PTC Pharmacovigilance Department within 24 hours on a SAE Report Form only when associated with an SAE.

7.3.15. Safety Oversight

An independent DSMB will be utilized during the study. The DSMB will closely monitor potential emerging safety signals in all subjects in the study throughout their study participation, including the planned transition without interruption in treatment from Part A to Part B of the study.

8. STATISTICAL CONSIDERATOINS

A Statistical Analysis Plan (SAP) will be prepared before database lock.

8.1. Statistical Hypotheses

For the primary efficacy endpoint, the null hypothesis of this study is that the subject ranks based on the composite survival and change from baseline in ALSFRS-R after the 24-week Treatment Period are the same in the PTC857 group and in the placebo group versus the alternative that they are different.

The primary efficacy endpoint will be analyzed on the ITT1 Analysis Set at the significance level of 0.05 (2-sided). If p<0.05, then the study will be declared positive.

8.2. Sample Size Determination

For the primary efficacy endpoint, the combined assessment of ALSFRS-R and survival after 24 weeks of treatment, 307 subjects in the ITT1 Analysis Set (205 in the PTC857 group and 102 in the placebo group, based on a 2:1 randomization ratio) will provide approximately 85% power to detect a treatment difference of 2.5 points with a standard deviation of 5.3, based on a 2-sided 0.05 level Joint Rank Test, and assuming 24-week survival rates of 96.5% and 95% in the PTC857 and placebo groups, respectively. Data from the 2 recently concluded clinical studies in ALS reported overall death rates of 5% and 0% (Edaravone (MCl-186) ALS 19 Study Writing Group 2017, Paganoni 2020). In addition, the edaravone study reported a standard deviation of 5.3 points for the ALSFRS-R score at Week 24, among treated subjects. Assuming approximately 10% of randomized subjects will not meet the ITT1 Analysis Set definition, then approximately 340 subjects will be randomized to ensure that 307 subjects are randomized into the ITT1 Analysis Set. Given that the primary analysis incorporates deaths as a combined endpoint, and a fully imputed analysis dataset is utilized in the analysis, additional sampling for missing data is not planned.

8.3. Population for Analyses

Intent-to-Treat 1 Analysis Set: All subjects who are randomized after the Screening Period and take at least 1 dose of double-blind study drug in the Treatment Period and who have a decrease in the ALSFRS-R score of ≤4 points during the Screening Period will be included in the ITT1 Analysis Set. Subjects will be analyzed according to their randomized treatment. The ITT1 Analysis Set will be used for analysis of the primary endpoint.

Intent-to-Treat 2 Analysis Set: All subjects who are randomized after the Screening Period and take at least 1 dose of double-blind study drug in the Treatment Period will be included in the ITT2 Analysis Set. Subjects will be analyzed according to their randomized treatment.

Per Protocol Analysis Set: All subjects in the ITT1 Analysis Set who have no major protocol deviations that affect the validity of the efficacy measurements will be included in the PP Analysis Set. The PP Analysis Set will be used for sensitivity analysis of the efficacy endpoint. The criteria for inclusion in the PP Analysis Set will be finalized prior to study unblinding and detailed in the SAP.

Safety Analysis Set: All subjects in the ITT2 Analysis Set who receive at least 1 dose of study drug will be included in the Safety Analysis Set. Subjects will be analyzed according to the actual treatment received.

PK Analysis Set: All subjects in the ITT2 Analysis Set who have at least 1 measurable plasma or CSF PTC857 concentration will be included in the PK Analysis Set.

8.4. Statistical Analyses

Detailed methodology for summary and statistical analyses of the data collected in this study will be documented in the SAP. The analysis of the data for the Treatment Period (Part A) (ie, up to the Week 24 Visit) will be produced after the lock of database for Part A. The LTE Period (Part B) of the study will continue for all subjects participating in that part, and results from Part B will be reported separately. The Continued LTE Period (Part C) of the study will continue for all subjects participating in that part, and the results from Part C will also be reported separately.

8.4.1. Primary Efficacy Endpoint

For the primary efficacy endpoint, subject ranks based on the combined assessment of function and survival (CAFS) ranking method, will be analyzed when all subjects in the ITT1 Analysis Set finish the Treatment Period (Part A). This analysis will be performed using an analysis of covariance (ANCOVA) model following multiple imputation. Subjects who discontinue from the study prior to Week 24 will have their Week 24 ALSFRS-R score imputed using multiple imputation. The ANCOVA model will include the following covariates: treatment arm (PTC857 and placebo), baseline ALSFRS-R score, the amount of change in the subject's ALSFRS-R score during the Screening Period (<1, 1-2, and 3-4 points total loss), and standard-of-care exposure with rank scores as the response variable. A p value for the difference will be presented.

The analysis of the primary efficacy endpoint will occur when the Part A database is locked. Sensitivity and subgroup analyses of the primary efficacy endpoint will be described in the SAP.

8.4.2. Secondary Efficacy Endpoints (Part A)

Change from baseline in ALSFRS-R at Week 24 will be evaluated by means of a mixed model repeated measures analysis using all available ALSFRS-R scores up to Week 24. The model will include fixed effects for treatment (PTC857 and placebo), baseline ALSFRS-R value, time of collection (actual week at the visit as a categorical variable), time-by-treatment interaction, time-by-baseline ALSFRS-R interaction, the amount of change in the subject's ALSFRS-R score during the Screening Period (<1, 1-2, and 3-4 points total loss), standard-of-care exposure, TRICALS risk profile, and TRICALS risk profile by time interaction as covariates. The unstructured covariance matrix (UN) will be used in the model. Other types of covariance matrices will be explored in the case of non-convergence of the UN. Subjects with no post-baseline results for the outcome variable will be excluded. This analysis will be performed for the ITT1 and ITT2 analysis sets.

Analysis of other secondary endpoints and sensitivity analyses will be specified in the SAP.

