4.6. Multiplicity

A fixed sequence testing procedure will be employed for selected efficacy endpoints. If the primary endpoint is statistically significant at a 2-sided 0.05 level, the secondary endpoints will then be tested sequentially in the order listed below, each at a 2-sided 0.05 alpha level. Testing within the specified sequence will stop if a null hypothesis in the sequence fails to be rejected.

- (1) Change from baseline in ALSFRS-R at Week 24 in the ITT1 analysis population
- (2) Change from baseline in ALSFRS-R at Week 24 in the ITT2 analysis population
- (3) Subject ranks based on the CAFS at Week 24 in the ITT2 analysis population
- (4) Change from baseline in total score of the Amyotrophic Lateral Sclerosis Assessment Questionnaire (ALSAQ-40) after 24 weeks of treatment, in the ITT1 analysis population
- (5) Change from baseline in log transformed plasma NfL, in the ITT1 analysis population There will be no interim analysis.

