5. EFFICACY ANALYSIS

5.1. Analysis of the Primary Efficacy Endpoint

The primary efficacy variable, subject ranks based on the combined assessment of function and survival (CAFS) after 24 weeks of treatment will be performed using an analysis of covariance model (ANCOVA) following multiple imputation. The estimand framework described in Section 3.3.1 will be used. The ANCOVA model will contain the following main effects: treatment (PTC857 or placebo), the amount of change in the subject's ALSFRS-R score during the Screening Period (<1, 1-2, or 3-4-points total loss), TRICALS risk profile (continuous), use of Approved Background Therapy for ALS (Yes [either riluzole, edaravone, or sodium phenylbutyrate/taurursodiol], No). Baseline ALSFRS-R score (continuous) and The TRICALS risk profile (continuous) will be included as covariates.

Subjects who discontinue from the study prior to week 24 will have their week 24 ALSFRS-R score imputed using the same datasets described in Section 5.5.1.2. In each of the 100 imputed datasets, subjects who die will have their death day (study day) incorporated as part of the combined assessment of function and survival.

The p-value for the treatment comparison (PTC857 versus Placebo) at week 24, estimate of LSMEANS for the treatment differences (PTC857 – Placebo), and the two-sided 95% confidence interval of the LSMEANS difference will be presented for the ITT1 analysis set (obtained from PROC MIANALYZE in SAS). If the p-value for the treatment arm comparisons at week 24 is less than 0.05, then the study will be declared as positive.

This analysis will also be repeated for the ITT2 analysis set and a nominal p-value for treatment arm comparison at week 24 presented.

In addition, averaged win probability (Rubin's rule) and a win-odds, will also be presented.

$$\label{eq:winprobability} Win\ probability(\theta) = 0.5 + \frac{\bar{R}_i - \bar{R}_j}{N_i + N_j} & Where: \\ \bar{R}_i = \ mean\ ranks\ for\ treatment\ groups_{i,j} \\ N_i = \ No.\ subjects\ in\ treatment\ groups_{i,j} \\ \end{cases}$$

$$Win\ odds = \frac{\theta}{(1-\theta)}$$

Given the difficulties in interpreting and quantifying the treatment effect from the CAFS analysis, results from the MMRM analysis in ALSFRS at week 24 (Section 5.5) will be used to describe the treatment effect in terms of loss of function). Similarly, survival differences will be described using results from the Survival analysis (Section 5.7)

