5.5.1. Change from Baseline in ALSFRS-R

5.5.1.1. Mixed Model Repeated Measures (MMRM)

Change from baseline in ALSFRS-R at Week 24 will be evaluated by means of a mixed model repeated measures analysis using all available ALSFRS-R scores up to Week 24. The estimand framework described in Section 3.3.2 will be used. The model will include fixed categorical effects of treatment (PTC857 or placebo), use of approved background therapy for ALS (Yes vs No), the amount of change in the subject's ALSFRS-R score during the Screening Period (<1, 1-2 or 3-4 points total loss), time of collection (nominal week at the visit as a categorical variable), as well as the continuous, fixed covariates of baseline ALSFRS-R, and The TRICALS risk profile. In addition, the following interaction terms will be included: Time by treatment, time by baseline ALSFRS-R, and TRICALS risk profile by time. Subject will be included as a random effect. The Restricted Maximum Likelihood (REML) estimation approach will be used with the variance-covariance structure set as unstructured (UN). Other types of covariance matrices will be explored in the case of non-convergence of the UN. Subjects with no post baseline results for the outcome variable will be excluded. This analysis will be performed for both the ITT1 and ITT2 analysis sets.

Observed and change-from-baseline values will also be summarized descriptively at each visit.

In supplementary analyses, score changes from baseline at Week 24 for the ALSFRS-R subdomains will be analyzed under the same estimand framework where MMRM models will be used to implicitly impute missing data. Nominal P-values for the treatment arm comparison, estimate of LSMEANS for the treatment differences (PTC857 – Placebo) at Week 24, and the two-sided 95% confidence intervals of the LSMEANS difference will be presented.

5.5.1.2. Analysis of Covariance Model (ANCOVA) with Multiple Imputation:

An additional analysis to evaluate change from baseline in ALSFRS-R will be performed using an analysis of covariance model (ANCOVA) following multiple imputation (MAR assumption). Missing ALSFRS-R scores, (including those missing due to death) will be imputed using multiple imputation (MI), 100 imputations will be generated using PROC MI in SAS. The Fully Conditional Specification (FCS) model using the regression method will be used.

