5.5.2. Analysis of Other Continuous Secondary Endpoints

The following secondary (continuous) endpoints will be analyzed for both the ITT1 and ITT2 analysis sets under the estimand framework described in Section 3.3.2, where an MMRM is used to implicitly impute missing data. The MMRM models will include fixed categorical effects of treatment (PTC857 or placebo), use of approved background therapy for ALS (Yes vs No), the amount of change in the subject's ALSFRS-R score during the Screening Period (<1, 1-2 or 3-4 points total loss), time of collection (nominal week at the visit as a categorical variable), as well as the continuous, fixed covariates of baseline endpoint variable (e.g., ALSFRS-R, ALSAQ-40), and The TRICALS risk profile. In addition, the following interaction terms will be included: Time by treatment, time by baseline value of endpoint, and TRICALS risk profile by time.

P-values for the treatment arm comparison at week 24, estimate of LSMEANS for the treatment differences (PTC857 – Placebo), and the two-sided 95% confidence intervals of the LSMEANS difference will be presented:

- Change from baseline in ALSFRS-R in the Intent-to-Treat 2 (ITT2) Analysis Set after 24 weeks of treatment.
- Quality of life as assessed by Amyotrophic Lateral Sclerosis Assessment Questionnaire (ALSAQ-40) after 24 weeks of treatment, for ITT1 and ITT2 analysis sets.
- Change from baseline in Modified Norris Scale total score, limbs score and bulbar score at Week 24, for ITT1 and ITT2 analysis sets.

• Change from baseline in slow vital capacity (SVC) as assessed by pulmonary function tests (PFTs) after 24 weeks of treatment for the ITT1 and ITT2 analysis sets.

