14. APPENDIX 4: SAS CODE

Mixed Model Repeated Measure

The following is example SAS syntax for producing least squares estimates, for the MMRM analysis:

```
proc mixed data=ALSFRS_LONG method=reml;
  class ID TRTRND(ref="0") STADCARE(ref="3") CHANGE(ref="<1")
TIME(ref="baseline");
  model DELFRS = TIME VALUEBL CHANGE STADCARE TIME*TRTRND TIME*VALUEBL TRP
  TIME*TRP / ddfm=kr solution;
  repeated TIME / type=UN subject=id;
  lsmeans trtrnd*TIME /cl pdiff=control('0' '5')cl;
  run;</pre>
```

where id is the subject identifier, trtrnd is the randomized treatment arm, stadcare is a factor variable for the SoC stratification group at baseline, change is the amount of change in the subject's ALSFRS-R score during the Screening Period, time is the categorical variable for study visit, Valuebl is the baseline ALSFRS-R score, TRP represents the TRICALS risk profile at baseline, and the response variable DELFRS is the change from baseline in ALSFRS-R score.:

ANCOVA with Multiple Imputation

SAS code for the ALSFRS-R endpoint at 24 weeks:

```
proc mi data = ALSFRS_DATA out = ALSFRS_DATA_OUT
    seed = 20221219 nimpute = 100 noprint;
    class trtrnd stadcare change sex;
    var trtrnd Valuebl change stadcare sex age trp
    ALSFRS_R_4 ALSFRS_R_8 ALSFRS_R_12 ALSFRS_R_16 ALSFRS_R_20 ALSFRS_R_24;
    fcs reg(ALSFRS_R_4 ALSFRS_R_8 ALSFRS_R_12 ALSFRS_R_16 ALSFRS_R_20
    ALSFRS_R_24);
    run;
```

The next set of code performs the analyses for the ALSFRS-R 24-week endpoint:

```
proc reg data=ALSFRS_DATA_OUT utset=outreg covout noprint;
  model ALSFRS_24 = trtrnd Valuebl change stadcare TRP;
  by _Imputation_;
  run;
```

This step will combine the results:

```
proc mianalyze data=outreg;
  modeleffects Intercept trtrnd Valuebl change stadcare TRP;
  run;
```

Pattern Mixture Model

The strategy implemented to carry out the control-based PMM assumes that all other variables, except ALSFRS-R, with missing data are first imputed using the FCS approached outlined in the previous sensitivity analysis, with 100 imputation datasets. These data are stored in DATAIN_IMP0, which contains a variable _Imputation_ to distinguish between multiple copies of the original input data. In the next step missing ALSFRS-R at the first time point will be imputed (the first time-point that has some missing data). To use the control-based imputation

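### The Part A ALSFRS-R MMRM gives the screening-decline stratum one effect common to all visits, so the Week 24 standard error tends to be modestly conservative

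*Protocol*

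**What the plan says.** Randomization is stratified by points lost on the ALSFRS-R during screening: <1, 1-2, 3-4 and >4 (protocol 5.3.1). ITT1 keeps subjects who lost 4 points or fewer; ITT2 keeps all randomized and dosed subjects.

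Three places specify the ALSFRS-R MMRM, and they agree:

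- Protocol 8.4.2 lists "time-by-treatment interaction, time-by-baseline ALSFRS-R interaction, the amount of change in the subject's ALSFRS-R score during the Screening Period", the stratum having no interaction with time.
- SAP (Part A) 5.5.1.1 names the interactions as "Time by treatment, time by baseline ALSFRS-R, and TRICALS risk profile by time".
- The model statement in SAP Appendix 4 begins "TIME VALUEBL CHANGE STADCARE TIME*TRTRND TIME*VALUEBL TRP" and ends with TIME*TRP. There is no TIME*CHANGE.

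The covariance is unstructured over six post-baseline visits (Days 29 to 169). SAP 4.6 puts this model's Week 24 result first and second in the fixed sequence after the primary endpoint, as "1) Change from baseline in ALSFRS-R at Week 24 in the ITT1 analysis population" and "2) Change from baseline in ALSFRS-R at Week 24 in the ITT2 analysis population", "each at a 2-sided 0.05 alpha level". SAP 5.1 adds that "results from the MMRM analysis in ALSFRS at week 24 (Section 5.5) will be used to describe the treatment effect", because the CAFS result is hard to interpret.

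**The concern.** Screening decline is a measure of rate of loss. If it predicts later decline, its effect on change from baseline should be small at Week 4 and largest at Week 24. One coefficient for all visits cannot follow that. With an unstructured covariance, the coefficient is weighted towards the early, low-variance visits. Error in the Day 1 score also matters there: a Day 1 score that is too low exaggerates the screening loss and makes later change look better. The fitted coefficient may therefore say little about Week 24.

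The stratum's Week 24 effect is then left largely in the residual variance. Stratified randomization has already removed that variation from the treatment comparison, so the model reports more uncertainty than there is. At stake are some power at the first two gated secondary tests and the width of the interval that will describe the effect in ALSFRS-R points.

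**Working it through.** **The plan's own figure.** The documents give one power figure, about 85% for the primary joint rank test, and none for the MMRM. With 205 and 102 subjects, a 2-point difference and SD 5.3 (SAP 1.5), the two-sample SE is 5.3 × √(1/205 + 1/102) = 0.642, and power is Φ(2/0.642 − 1.96) = 87.6%. A joint rank simulation with survival of 96.5% and 95% gives 85.4%. The stated figure is reproduced.

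**Simulation with a set stratum effect.** This used 2:1 blocks within strata, six visits, Week 24 SD 5.3, a stratum effect growing linearly with time, REML with unstructured covariance, and 60 runs per setting. R² is the share of Week 24 variance that the stratum explains beyond baseline and TRICALS. It is an assumption. ITT1 without dropout:

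| R² | Planned SE | SE with TIME*CHANGE | Ratio |
|---|---|---|---|
| 0 | 0.644 | 0.644 | 1.000 |
| 2% | 0.644 | 0.638 | 1.010 |
| 5% | 0.644 | 0.628 | 1.025 |
| 10% | 0.642 | 0.611 | 1.050 |
| 20% | 0.637 | 0.577 | 1.104 |

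ITT2 ratios are nearly the same, and 15% dropout changes them little. At R² = 10% the empirical spread of the estimate is 0.656 (planned) and 0.655 (with the term), so only the reported SE differs. At the same R² the SE with no stratum term is 0.6463, against 0.6417 as planned and 0.6114 with the interaction. The planned term thus recovers 0.0046 of an available 0.0349, about 13%.

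**Simulation with random slopes and measurement error.** Here the strata are formed from error-prone scores. Assumptions not in the documents: pre/post slope correlation 0.5-0.7 and per-assessment measurement SD 0.8-2.0. The planned SE was 1-9% too large in ITT1 and 1-13% in ITT2. The planned coefficient for 3-4 versus <1 points was about +0.7 to +1.4, while the Week 24 value was negative in 5 of 6 ITT1 settings. In a further random-slope run the ITT1 ratio was only 1.002 at measurement SD 2.0. It reached 1.17 only at SD 0.6, where the simulated Week 24 SD was 3.15 rather than 5.3.

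**What an oversized SE costs.** Let s be the true SE, r the ratio of reported to true SE, and δ = 2.

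- Power as planned = Φ(δ/s − 1.96r); power if calibrated = Φ(δ/s − 1.96).
- Equivalent sample loss = 1 − [1 − 1.96(r − 1)/(δ/s)]².
- Type I error = 2[1 − Φ(1.96r)].

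At slope correlation 0.7 and measurement SD 1.3, s = 0.589 and the reported SE is 0.617, so r = 1.0475 and δ/s = 3.396.

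- Power is 91.0% against 92.4%, a loss of 1.4 points (simulated: 90.6% and 92.2%).
- Sample loss is 1 − (1 − 0.0931/3.396)² = 5.4%.
- Type I error is 4.0% (simulated: 4.2%, against 5.2% with the term).

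With the same s, r = 1.02 gives a sample loss of 2.3% and r = 1.05 gives 5.7%. From the table, the power loss is 1.8 points at R² = 10% and 3.0 points at R² = 20%.

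**The case against.** The strongest reply is that nothing is invalid and the gain may be negligible. Most of it stands.

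- **Size.** What matters is prediction beyond TRICALS, which already contains an ALSFRS-R progression rate and has a by-time term. The documents give no figure for the remainder. It need not be nil: Appendix 3 computes that rate from the screening score and diagnostic delay, so the eight-week screening change is not in it.
- **Gating.** Step 1 is tested only after the primary succeeds. Assuming 85% primary power and a correlation of 0.85-0.95 between the two test statistics, the chance of passing both falls by only 0.3-0.6 points in the worked example and 0.5-1.2 points at R² = 20%.
- **An adjusted analysis exists.** The ANCOVA with multiple imputation in SAP 5.5.1.2 uses one time point, so its stratum coefficient is a Week 24 coefficient. Its p-value is nominal, however, and it does not replace the gated test.

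A reader might square the SE ratio and infer a loss of 4-10% of the sample at an excess of 2-5%. That would hold only if the planned estimator were itself less precise; its spread is unchanged, so 2-6% is right.

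A reader might also carry the point to SAP 5.5.2, whose models use "Time by treatment, time by baseline value of endpoint, and TRICALS risk profile by time", and to the extension SAP. Neither was simulated. The 5.5.2 endpoints have two scheduled post-baseline visits in Part A and do not share the Day 1 ALSFRS-R error. The Week 160 model has 19 visits, so the term would cost 2 × 18 = 36 parameters with three levels or 3 × 18 = 54 with four, on top of a 19 × 19 unstructured covariance.

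**Conclusion.** The omission is real and consistent across protocol 8.4.2, SAP 5.5.1.1 and the code. Its consequence is a Week 24 SE that tends to be conservative: about 1-9% too large in ITT1 and 1-13% in ITT2 under the assumed slope correlations and measurement errors, and close to nil when measurement error is large. At an excess of 2-5%, the loss is roughly 2-6% of the sample and up to about 2 power points at the first gated secondary test, before allowing for the gate.

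The documents do not support a reading that the SE is too large in every case, that the treatment estimate is biased, or that type I error is inflated. The primary CAFS ANCOVA is fitted at a single time point and is unaffected. In SAP 5.1's use of the MMRM to describe the effect, only the interval is touched.

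The change is worth making because it is almost free and in these simulations did not materially raise the SE.

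**What to change.** Add a time by screening-decline-stratum interaction to the Part A ALSFRS-R MMRM in protocol 8.4.2 and SAP 5.5.1.1, and TIME*CHANGE to the model statement in Appendix 4, for both ITT1 and ITT2. For ITT2, name the >4-point level, which the present model text omits. Keep the sparse-strata fallback in SAP 5.5. Settle this before treatment codes are opened.

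The cost is (3 − 1) × (6 − 1) = 10 extra parameters in ITT1, with 307 subjects planned, and (4 − 1) × (6 − 1) = 15 in ITT2, with about 340. It needs no new data and leaves the estimand unchanged. Leave the SAP 5.5.2 endpoints and the extension-period model as they are unless a separate case is made for them.
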